The goal of this study is to investigate the applicability and utility of an innovative technology product such as WeReha to the home rehabilitation of stroke patients as an integrative solution to

a conventional exercise program and to assess its acceptance by the patient, caregivers and clinic professionals.

Patients will use WeReha for their home rehabilitation in addition to traditional treatments for up to 12 weeks. The Inclusion criteria for the study have been kept broad in order to assess these factors on a large enough scale, so as not to limit the usage of the device to a specific sub-group of patients. If patients enrolled are in a subacute phase (i.e. within the first 6 months after the stroke onset), they will be enrolled before leaving the hospital or the rehabilitation department and reaching their home. If patients are considered to be in their chronic phase (i.e. over 6 months after stroke onset), they will be enrolled during an outpatient treatment or on a volunteer basis.

Before starting the trial with WeReha, every patient enrolled will receive proper training from a person dedicated to the project (who will be referred to as the “dedicated figure”) appointed by the hospital and financially supported by the sponsor of the study.

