## Study goals and objectives

The goal of this study is to assess the acceptance and validity of a new technology such as WeReha for home rehabilitation of patients following a stroke episode either in sub-acute or chronic phase. The investigation will be conducted in two different countries: two sites in Northern Ireland and one in Italy.

This study is part of the EU funded Magic PCP project [5], where three different companies will perform similar types of study. Every company will be assigned from September 2018 a trust in Northern Ireland and a site in Italy from among the following: Hospital Le Torrette, Ancona, University D'Annunzio, Chieti, ASL3 Pinerolo, Torino. Once a company has received approval for funds to perform the study (before September 2018), it will also be assigned the site in Italy and then it will apply for the Ethical Committee of that site. Every company is also required by the Magic PCP project [5] to provide 75 devices per country (150 in total). From now on, we will refer to the number of patients relevant to the Northern Irish site..

Let us define the terms and list assumptions we will use throughout the protocol:

- “enrolled patient”: a patient is considered enrolled in the study if they are within the inclusion criteria and voluntarily accept to participate and sign the consent form
- “active week”: a week in which the patient has performed at least three sessions with WeReha for a minimum of 15 minutes each (as measured by the software)
- “active patient”: a patient that has used the device for at least 4 “active weeks”
- “maximum time frame of usage”: 20 weeks, according to patients and clinicians feedback collected during our feasibility study (see [Safety Consideration](#) section)
- “end of usage”: if the participant does not have four active weeks in the first eight weeks of usage or the patient has reached the “maximum time frame of usage” or the patient has voluntarily decided to interrupt the study (drop-off)

The study aims to evaluate as a primary outcome quantifiable measure, the acceptance of technology, through analysis of the following:

- number of enrolled patients at the end of the trial period will be evaluated in order to understand the degree of acceptance of a technology such as WeReha, with the minimum target of 50 patients.
- number of “active weeks” with the device among the patients enrolled

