- ii)     ii) how to position the sensor inside it,
- iii)     iii) how to move the object in order to reach the game’s target.

Once the sensor is worn or positioned inside an object, before starting the game, the patient is guided through a calibration phase to measure the sensors initial orientation in the space which acts as a reference position for all the movements recorded during the game. This process not only makes the measures more accurate but also nullifies any sensor wrongly positioned when worn (i.e. sensor overturning, rotations, inclinations respect to the body frontal plane).

In this pilot study investigators will recruit as many patients as possible as defined within the inclusion and exclusion criteria. There will be 75 devices available at the site from September 2018 to December 2019. Each patient will be provided with a WeReha device including the tablet and its charger, the inertial sensor and its charging station and cable, a kit of elastic straps together with a Velcro pocket and the 3 plastic objects. Every device can be used twice in order to assess as many patients as possible, providing a new set of straps and smart objects (that are to be considered single user only) and cleaning the other components by following specific and simple instructions provided by CoRehab.

Participants will be consented following a diagnosis of stroke and will keep the device for a maximum of 20 weeks following discharge from the hospital setting. This amount of time has been decided following review by clinicians and therapists during our earlier feasibility work. After that the tablet and the sensor will be collected, cleaned to ensure no cross contamination and meeting infection control guidelines within each Trust and made available for further use... The elastic straps with the pockets and the smart objects are the only personal and single use components, which will be disposed of after use... Secondary outcomes will only be assessed on “active patients”.

There will be a WeReha server available as a cloud solution, compliant with NCSC Cloud Security Principles, on which the web application will run and all the data will be collected whenever a patient’s device is connected to the internet. It is important to highlight that internet connection is not mandatory for the device to work properly as it will propose exercises to the patient as they were prepared initially after patient’s discharge. Then, whenever the device is

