Only after the dedicated figures have enrolled the patient and the signed consent form is completed will a participant be registered on the WeReha system through the dedicated clinical web application. Patient and the caregiver(s) will then receive appropriate training from the dedicated figures with a device similar to the one they will be using at home. The training will take place in the facility where the patient has been enrolled and it will be carried out by the dedicated figure. This will take the form of an education session aimed to provide the patient and the caregiver with all the technical information required for the correct usage of the device. All participants will also be taught how the biofeedback exercises works in terms of games graphics, goals, bonus, scores as well as how to understand if the movement performed is correct or not. The caregiver is instructed in helping and supporting the patient when required and how to make contact with the supervisor in case assistance for the device is required. Both the patient and the caregiver, before leaving the facility, will be provided with a user manual for WeReha's usage at home. Based on our experience during the feasibility work, this training will last a minimum of 30 minutes up to a maximum of 60 minutes). The dedicated figure will then input the information about the patient into the WeReha web application, together with the results obtained in scores, and scales, resulting in the creation of a rehabilitation protocol, validated with rehabilitation professionals, which will then will be assigned to the patient. In cases where the participant remains in hospital for longer than expected, they will be permitted to use the device in this setting. Use of the device in this setting will not be included in the 20 weeks of usage.

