Following discharge, participants will be reviewed in their own environment by the PI to ensure that the device is set up appropriately so that they can perform the exercises assigned. Participant usage of the device will be monitored at eight weeks. If at this stage the participant has not had four active weeks then the PI will review the patient with the expectation of the device being returned. In certain cases patients may have been unwell for a prolonged period and unable to use the device and it will be left to the PI to decide whether to remove the device or to allow the patient to continue using it for the full 20 weeks. All participants recruited to the study will be asked to complete the Technology Assessment Model questionnaire. After 20 weeks, the patient will return the WeReha device and the designated person will complete final assessments (clinical evaluation and questionnaires).

Identifiable data will be retained for the whole research study period. The data retention policy is clearly stated in the Patient Information Sheet. Since the Community Stroke Team provides therapy to patients, the team will highlight any capacity/ safety issues at any time and will then manage the patient to ensure safety.

Once the WeReha is returned to the hospital after being used by a patient, the dedicated person will follow a specific procedure in order to make the device available for any future usage by another patient. This procedure consists of resetting data through the specific button in the administration area of the software and cleaning as per infection control procedures for all the

reusable HW components. Also, new single use components (straps and smart objects) will be prepared for a new patient, so that the device is completely reusable.

Throughout the study, WeReha will suggest exercises in different forms to support rehabilitation of the most important body functions.

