## Duration of the study and patient's timeline

The total duration of the study is expected to be approximately 1 year and 4 months, starting at the beginning of September 2018 and ending at the end of December 2019.

Each patient will be required to keep the device for 20 weeks following discharge after which they will return the WeReha device to the hospital. In cases where a participant uses the device for

four of the first eight weeks the device has been assigned, the patient's generated output will be considered as valid.

When a patient starts the evaluation period, some clinical measures will be taken, as well as when (s) he returns the device. Such clinical evaluations are specified in the 'Methodology' section.

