## Follow-Up

The product will be provided for a maximum of 20 weeks following discharge to the patient, after which the device will be returned to the PI or the trial site for further usage. Patients are not required to have additional follow up after the study term is completed.

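### The 20-week device period and the four-active-weeks-in-eight rule have different start dates, none is stated for patients enrolled after discharge, and the exclusion of in-hospital use is not carried into the active-week counts

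*Combined protocol and SAP*

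**What the plan says.** Two windows are involved.

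**The 20-week device period.** Every section that names a start date uses discharge. Under Study Design, participants "will keep the device for a maximum of 20 weeks following discharge from the hospital setting". Under Duration of the study and patient's timeline: "Each patient will be required to keep the device for 20 weeks following discharge". Under Follow-Up: "The product will be provided for a maximum of 20 weeks following discharge to the patient". Methodology fits with this. It allows device use during a hospital stay that runs longer than expected and adds: "Use of the device in this setting will not be included in the 20 weeks of usage".

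**The eight-week rule.** Study goals and objectives ends usage "if the participant does not have four active weeks in the first eight weeks of usage". Duration of the study treats a patient's data as valid when the device was used in "four of the first eight weeks the device has been assigned". Methodology says "Participant usage of the device will be monitored at eight weeks", with no start date in that sentence.

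**Who is in scope.** For chronic patients, more than six months after onset, the Project summary says "they will be enrolled during an outpatient treatment or on a volunteer basis". Study Design also admits patients already discharged from the stroke units to the community.

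**What is counted.** Study goals and objectives defines an active week by three or more software-measured sessions of 15 minutes or longer, and an active patient by four such weeks. Neither definition names a setting or a start date.

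**The concern.** The study asks whether patients accept the device for rehabilitation at home. Under Data Management and Statistical Analysis, the primary outcomes receive no statistical analysis and are judged by whether the KPIs are met, so the counting rules determine the primary result.

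The start dates and the treatment of in-hospital sessions feed:
- the KPI of at least 40 active patients;
- the KPI of 8 active weeks on average;
- the weekly minutes KPI, which is measured in active weeks only;
- the drop-off count;
- the validity of a patient's data;
- the secondary outcomes, which are assessed in active patients only.

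If two sites read the rules differently, the same usage record can yield an active patient at one and a drop-off at the other. Sessions done in hospital, near staff, could also be credited to home acceptance.

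**Working it through.** The plan gives no figure on this point to reproduce. The check compares the sections and applies calendar arithmetic.

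**1. Start dates side by side**

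| Rule | Section | Start date |
|---|---|---|
| 20 weeks | Study Design; Duration of the study; Follow-Up | discharge |
| 20 weeks | Study goals and objectives (definitions) | none stated |
| Four weeks in eight | Duration of the study | device assignment |
| Four weeks in eight | Study goals and objectives | usage, not defined further |
| Eight-week check | Methodology | none in the sentence; the paragraph opens with review after discharge |

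Duration of the study uses discharge for one window and assignment for the other. The two dates differ for any patient given the device in hospital, and for any patient enrolled after discharge.

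**2. Patients enrolled after discharge**

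Six months is 365.25 / 2 / 7 = 26.1 weeks. On a literal discharge start, a patient enrolled at the earliest chronic time point has

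weeks left = 20 − (26.1 − inpatient weeks).

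This is zero at an inpatient stay of 26.1 − 20 = 6.1 weeks. The documents do not give length of stay, so the range is an assumption:

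| Assumed stay (weeks) | Weeks left of 20 |
|---|---|
| 1 | −5.1 |
| 2 | −4.1 |
| 4 | −2.1 |
| 6 | −0.1 |
| 8 | +1.9 |
| 12 | +5.9 |

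Later enrolment leaves less. Even a 12-week stay leaves fewer than the eight weeks that the check needs.

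**3. In-hospital use and the eight-week rule dated from assignment**

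Duration of the study speaks of using the device in four weeks, not of active weeks; I read it as the same rule as in the definitions. Let h be the weeks in hospital after assignment.

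- Home weeks inside the eight = 8 − h.
- If in-hospital weeks count and are all active, home active weeks still needed = max(0, 4 − h).
- If they do not count, the rule can be met only when 8 − h ≥ 4, that is h ≤ 4.

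| h | Home weeks inside the eight | Home active weeks needed if hospital weeks count | Rule can be met if they do not count |
|---|---|---|---|
| 0 | 8 | 4 | yes |
| 2 | 6 | 2 | yes |
| 4 | 4 | 0 | yes, if every home week is active |
| 5 | 3 | 0 | no |
| 8 | 0 | 0 | no |

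From h = 5 the two readings give opposite answers for the same patient.

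**4. Effect on the KPIs per patient**

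One reclassified patient moves the active-patient count by 1 against the target of 40. Four in-hospital active weeks in one patient add 4/50 = 0.08 weeks to the average if 50 patients are in the denominator, or 4/40 = 0.10 weeks if 40 are.

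**The case against.** The strongest reply is that sensible reading removes most of the difficulty.

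- A patient cannot keep a device before receiving it, and the definitions cap usage at 20 weeks without mentioning discharge. Chronic patients are deliberately included, and nothing says a device would be refused or recalled because of an old discharge.
- The definitions use the word usage for both limits, and Methodology takes in-hospital use out of the 20 weeks. Read together, in-hospital use falls outside the eight weeks too. The eight-week check also follows a sentence about review after discharge.
- In-hospital use is an exception for prolonged stays. At eight weeks the PI reviews the patient and may allow continued use, so a failed check has no automatic consequence.
- The eight-week check is not a listed primary outcome, and the active-patient definition has no eight-week limit.

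Much of this stands. A reader might infer that the window is closed to chronic patients; that takes the wording on keeping the device too literally and depends on an unstated length of stay. What is established is that these patients have no stated start date. A reader might also infer one clock with three origins, including first use. The documents contain two windows, the 20-week one is consistently dated wherever it is dated at all, and no section names first use. Nor does any section say that in-hospital sessions count towards home use; the definitions are silent.

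The reply does not dispose of the assignment wording under Duration of the study, which decides whether a patient's data are valid and cannot be read as starting at discharge. It supplies no written start date for patients enrolled after discharge. It relies on carrying Methodology's exclusion into definitions that do not mention it. The eight-week rule can also affect the KPIs indirectly, because a patient whose device is returned at that point accrues no further active weeks.

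**Conclusion.** The concern holds as an inconsistency between stated rules and a gap in the counting definitions. The eight-week rule has two differently worded starts, neither of which is the discharge date used for the 20 weeks. Patients enrolled after discharge have no stated start for either window. The exclusion of in-hospital use is written for the 20 weeks only.

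For an affected patient the classification can reverse: four active weeks in hospital could satisfy the active-patient definition with no home use, while five or more in-hospital weeks after assignment could make the eight-week rule impossible to meet. Across the study the size is unknown, because the documents give neither length of stay nor the expected number of inpatient users or late enrollees. The 6.1-week threshold assumes enrolment exactly at six months and a literal discharge start. The documents do not show that the KPIs will be inflated; they leave the counts open to more than one reading. That is worth correcting before the KPIs are read, since the KPIs are the whole primary assessment.

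**What to change.** Reconcile Study goals and objectives, Study Design, Methodology, Duration of the study and Follow-Up so that each window has one stated start date that exists for every enrolled patient, including those enrolled after discharge. The two windows may start on different dates if both are written down. How long a patient keeps the device, and what follows from the eight-week review, are for the sponsor to reconcile.

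For the analysis:
- Record the device-receipt date and, where relevant, the discharge date. Receipt is already when the baseline scores are taken.
- Apply Methodology's exclusion to the active-week, active-patient and eight-week counts, so that they use home sessions only. In the eight-week count, leave out the in-hospital time as well as the in-hospital sessions; otherwise a long stay makes the rule unattainable, as shown above.
- Report in-hospital use separately.

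A single receipt date for everything would not be enough, because in-hospital sessions after receipt would then fall inside the window.

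The cost is wording, one or two dates per patient, and a home or in-hospital marker on the exported session data, since the anonymised record described in Annex A lists neither date. Some in-hospital weeks would no longer count towards the KPIs.

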- average minutes of exercise per day conducted with the technology as an objective measure for activity participation
- acceptance of technology, based on the Technology Acceptance Model / TAM as in [11] and [33] provided to patients at the end of the study (see [Annex B](#)).

All previous measures will be evaluated in general and for 6 different age-gender groups (male and female below 55, between 55 and 70, above 70).

As secondary outcome measures we will assess objective scales and scores typical for stroke rehabilitation:

- the Barthel index (see [10], [19], [6], [8])
- the Modified Rankin Score (see [19], [30], [7], [8])
- 

These scores will be compared with standard values and the goal is to show equivalency or improvement from those standard values after the treatment with WeReha.

In addition, we want to demonstrate the logistical and economic benefits of the deployed solution. Dedicated figures (a nurse or physiotherapist hired to run the Clinical Trial research study as explained in the Methodology section) will objectively measure the time taken to training patients and caregivers before leaving the trial site with the device and the number of times patients contact the sponsor for technical assistance.

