#### **Primary Outcome Measures:**

- Total number of patients enrolled -> KPI: minimum 50 patients enrolled;
- Total number of active patients -> KPI: minimum 40 active patients;
- Total number of patients who drop off, meaning that started the study and had less than 4 active weeks
- Average number of active weeks for each patient: the average number of active weeks is evaluated as the total number of active weeks divided by the number of patients enrolled -> KPI: 8 weeks (excluding drop off before 4 weeks)
- Activity participation, measured in average minutes per day dedicated to exercises with WeReha (measured during active weeks only) -> KPI: min. 45'/week
- Acceptance of the rehabilitation platform WeReha by the patient, evaluated through a questionnaire completed at the end of the study by every participant who consents to the study (see attachment ... )
- Previous results will be analysed on different age/gender groups. Age groups are: <55, 55-70, 70-85 both for male and female, for a total of six groups. Target would be to enroll patients within these groups as homogeneously as possible, but since we cannot foresee patients distribution there are no KPIs set for this outcome

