#### **Secondary Outcome Measures:**

- Barthel index and Modified Rankin Score: change from baseline (measured when receiving the device) at the end of the rehabilitation treatment (when returning the device)
- Time dedicated by the specialised personnel to each patient for training to learn the WeReha device before leaving the trial site (measured in minutes/patient)
- Number of calls per week for clinical and technical assistance specific for the WeReha device, registered on a paper or software spreadsheet by the sponsor

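### Barthel and Rankin change is planned for active patients only, a group defined by device use after baseline, and no all-patients analysis is named

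*Combined protocol and SAP*

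**What the plan says.** The Study Design section states that "Secondary outcomes will only be assessed on" active patients. The Study goals and objectives section defines an active patient as "a patient that has used the device for at least 4" active weeks, an active week being one with at least three sessions of 15 minutes or more. The same section lists, among the events that end usage, "if the participant does not have four active weeks in the first eight weeks of usage". The Methodology section then has the investigator review such patients at eight weeks, expecting the device back, with discretion to let those who were unwell for a long period continue.

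On the clinical scores, Study goals and objectives says they will be compared with standard values and that "the goal is to show equivalency or improvement from those standard values". The primary outcome list sets a KPI of "minimum 40 active patients" against at least 50 enrolled. It also counts drop-offs, "meaning that started the study and had less than 4 active weeks".

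The secondary outcome list contains three items: Barthel and Rankin change from receipt to return of the device; "Time dedicated by the specialised personnel to each patient for training to learn the WeReha device before leaving the trial site"; and "Number of calls per week for clinical and technical assistance specific for the WeReha device". The statistical section describes a pre/post test for secondary outcomes but names no analysis population and no handling of missing scores.

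**The concern.** Active status is known only after several weeks of use, so restricting the analysis to active patients selects on something that happens after baseline. Patients who stop early may recover better, worse or the same as those who continue, and an active-only figure cannot show which. The drop-off count tells the reader how many patients are missing from the Barthel and Rankin result, but not how they fared.

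This matters because the scores are to be compared with standard values, and because the Project summary keeps eligibility broad so that findings are not tied to one sub-group. An active-only result brings a sub-group back in, this time chosen by adherence. The primary KPIs are unaffected.

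**Working it through.** The plan gives no sample size, power or effect size for the secondary outcomes, so there is no figure of its own to reproduce. The check is a comparison of passages followed by simple arithmetic.

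**1. Who is scored, and when**

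- Secondary Outcome Measures: change from receiving the device to returning it; no activity condition.
- Study Design, later paragraph: clinical measurements at study start and at device return; no activity condition.
- Duration of the study: clinical measures at start and at return; no activity condition.
- Annex A, anonymised patient record: start and end diagnostic data for each patient, used to measure the outcomes. Rankin is among the examples and Barthel is not.
- Methodology: final assessments are described after 20 weeks. Nothing is said about final scores at an earlier return.
- Study Design, the sentence at issue: active patients only.

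Most of the text therefore already places a score at return for everyone. Two gaps remain: the analysis set, and explicit scoring when the device comes back early.

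**2. Who is left out**

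The active-patient definition has no time window of its own. By default, however, a patient without four active weeks in the first eight reaches the end of usage and is expected to return the device. Eight weeks is thus the working limit, with investigator discretion as the exception.

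**3. Share left out and effect on the mean**

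Let f be the share of enrolled patients who are not active, A the mean change in active patients, N the mean change in the others, and D = A − N.

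All-patient mean = (1 − f)A + fN, so active-only mean minus all-patient mean = f × D.

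Inputs: 40 active and 50 enrolled are the KPI minimums; 75 is the number of devices; 75 × 2 = 150 if each device is used twice. D is not in the documents. A value of 5 Barthel points in either direction is assumed, only to show scale.

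| Enrolled | Active | Not active | f | Shift | Shift if D = ±5 (assumed) |
|---|---|---|---|---|---|
| 50 | 40 | 10 | 10/50 = 20% | 0.20 × D | ±1.0 point |
| 75 | 40 | 35 | 35/75 = 47% | 0.47 × D | ±2.3 points |
| 150 | 40 | 110 | 110/150 = 73% | 0.73 × D | ±3.7 points |

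If D = 0 the shift is zero in every row. The rows hold the active count at its minimum; more active patients would lower f.

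**4. Training time and calls**

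Read literally, the restriction covers these too, since both are listed as secondary outcomes. But training time is recorded for each patient before leaving the site, when nobody can yet be active. Study goals and objectives introduces the secondary measures as scales and scores, and brings in training time and contacts in a separate paragraph. That suggests the restriction was meant for the clinical scores.

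**The case against.** The strongest reply is that this is a single-arm pilot about acceptance. The restriction is stated openly, the drop-off count is reported, and four active weeks out of several months is a modest threshold. An all-patients pre/post figure would not isolate a device effect either, and the standard values are not specified, so the consequence for that comparison cannot be judged. All of this stands. It limits the weight of the point but does not supply the missing all-patients result.

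A second objection is that the Study Design section also uses the verb for assessing to mean taking measurements. The restriction could then mean that non-active patients are not scored at return at all, which would make the change one of data collection as well as analysis. This is possible, and it is why the fix asks for scoring at early return to be stated. A reader should not conclude that these scores will not be collected: three sections place them at return without any activity condition.

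Other stronger readings are also unsupported:

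- That the active-only figure must flatter the device. The documents give no sign for the difference between active and non-active patients.
- That 20% is a forecast or a ceiling. It is one combination of two separate minimum counts.
- That illness automatically excludes a patient. The investigator may let an unwell patient continue, and that patient may still become active.
- That training time and calls are definitely restricted. The text leaves this open and leans the other way.

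**Conclusion.** The point holds for Barthel and Rankin. As written, the plan yields a change score for adherent users only, sets it against standard values, and names no all-patients analysis beside it. The share left out is 20% at 40 of 50, 47% at 40 of 75 and 73% at 40 of 150; these are scenarios built from the protocol's own counts. The effect on the mean equals that share times an unknown difference, so neither its direction nor its size can be stated from the documents. Scoring at early return is not assured, because the Methodology section ties final assessments to the 20-week point. For training time and calls, only a clarification of scope is needed.

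**What to change.** Replace the restricting sentence in Study Design so that:

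1. Barthel and Rankin are scored at device return whatever the use, as the outcome list, the later Study Design paragraph and the Duration section already provide. State this in the Methodology section for early returns.
2. The main Barthel and Rankin change analysis covers all enrolled patients with a baseline score. Report how many return scores are missing and when each device was returned. Where scores are missing, describe the result as based on available return scores, because patients with return scores are not all patients.
3. Baseline Barthel and Rankin are tabulated for active and non-active patients.
4. The active-patient result is kept as a labelled supportive analysis.

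As a minor addition, state that training time and calls cover all patients trained or given a device.

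The cost is one replaced sentence, a short addition to the Methodology section and a few table columns. If the sponsor had intended not to score non-active patients, there is also one further assessment per early returner. The downsides are that some return scores will be missing and that early returners have shorter follow-up, so time of return must be read alongside the pooled change. The result remains an uncontrolled pre/post change.

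Separately, the maximum period with the device is 12 weeks in the Project summary and Safety Considerations, but 20 weeks in Study goals and objectives, Study Design, Methodology, Duration of the study and Follow-Up. These passages must be reconciled.
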